1.2.4. Study Rationale

Since 2013, after receiving approval by China Food and Drug Administration (CFDA) in treatment of ALK-positive advanced NSCLC in China, Xalkori[®] has become the standard of care for ALK-positive advanced NSCLC patients. Consequently, the treatment resistance to crizotinib becomes common in these patients. Acquired ALK kinase domain mutation and brain metastasis are the two major mechanism of refractory or resistance to crizotinib treatment.^{13,14,15}

To fulfill this treatment need in ALK-positive advanced NSCLC patients, second-generation of ALK inhibitors have been developed and showed treatment activity. In the near future, the second generation ALK inhibitors will be increasingly used in both crizotinib resistant and treatment naïve patients, and eventually, the resistance to 2nd gen ALK inhibitor will be more and more common.

The resistance to ALK inhibitors appears much more complex as a greater variety of mutations are found in crizotinib resistant patients. And in ceritinib or alectinib resistant patients, ALK mutation G1202R, V1180L and I1171T have all been observed.

Lorlatinib is a selective, brain-penetrant ALK TKI with potent activity against ALK and ROS1 fusions, including those harboring resistance mutations. Lorlatinib has demonstrated clinically meaningful anti-tumor activity in patients with brain metastases after treatment with ALK inhibitors including crizotinib.²⁷ Further, lorlatinib appears to be the only ALK TKI active against certain mutations that are the most difficult to inhibit after second-generation ALK inhibitor resistance, such as the G1202R mutation.²⁵

Lorlatinib has the potential to improve anti-tumor activity in ALK inhibitor resistance and refractory ALK-positive advanced NSCLC, based on its greater potency against ALK and its broad coverage against all known single point mutations that mediate resistance to crizotinib and second generation ALK inhibitors,²⁵ and able to cross the blood brain barrier. This study will evaluate the antitumor activities of lorlatinib in ALK inhibitor treated patients, which include both crizotinib treated and ALK inhibitors other than crizotinib treated patients.

1.2.5. Rationale for Starting Dosing Regimens

Lorlatinib starting dosing regimen will be 100 mg QD which was chosen as the RP2D based on the entirety of the safety, efficacy, and clinical pharmacology data available in B7461001 study.

Additional information may be found in IB.

2. STUDY OBJECTIVES AND ENDPOINTS

[figure not shown]
Primary Objective(s):	Primary Endpoint(s):

 To evaluate the anti-tumor effect of lorlatinib as a single agent as measured by ORR per RECIST v1.1 in locally advanced or metastatic ALK-positive NSCLC patients whose disease has progressed after crizotinib treatment. 	
 Objective Response (OR) in patients whose disease has progressed after crizotinib (Cohort 1) by independent central radiology (ICR) assessment per RECIST v1.1 (Appendix 3).
Secondary Objective(s):	Secondary Endpoint(s):

 To evaluate the anti-tumor effect of lorlatinib as a single agent as measured by ORR per RECIST v1.1 in locally advanced or metastatic ALK-positive NSCLC patients whose disease has progressed after ALK inhibitor treatment other than crizotinib. 	
 OR in patients whose disease has progress after ALK inhibitor treatment other than crizotinib (Cohort 2) as assessed by RECIST v1.1 per ICR assessment.

 To evaluate the PFS and OS in locally advanced or metastatic ALK-positive NSCLC patients whose disease has progressed after crizotinib and other ALK inhibitor treatment, respectively. 	
 Progression-free survival (PFS) as assessed by RECIST v1.1 per ICR assessment and investigator assessment and Overall survival (OS) in both Cohorts.

 To evaluate other antitumor activities in locally advanced or metastatic ALK-positive NSCLC patients whose disease has progressed after crizotinib and other ALK inhibitor treatment, respectively. 	
 Intracranial objective response (IC-OR), Duration of response (DoR), Duration of intracranial response (IC-DoR), Time to tumor response (TTR) as assessed by RECIST v1.1 per ICR assessment and investigator assessment in both Cohorts.

 To evaluate the safety and tolerability of lorlatinib treatment in locally advanced or metastatic ALK+ NSCLC patients whose disease has progressed after crizotinib and other ALK inhibitor treatment. 	
 Safety: AE; laboratory abnormalities; ECG, LVEF, CNS effects.

 To evaluate the pharmacokinetics (PK) of lorlatinib and potential pharmacokinetic (PK) /pharmacodynamics relationship for lorlatinib if appropriate. 	
 PK: parameters on Day 1 of Cycle 1 and at steady state: C_{max}, T_{max}, AUC_t, AUC_{tau} at steady state, AUC_{inf}, CL/F, Vz/F, $t_{1/2}$ and R_{ac} as data permit.
CCI	

3. STUDY DESIGN

This is a Phase 2, China only, multi-center (at approximately 30 sites), open-label, dual-cohort study, in which approximately 100 ALK-positive locally advanced or metastatic NSCLC patients will be enrolled to receive lorlatinib monotherapy according to the study design shown in [Figure 1](#). The patients should have (also see [Section 4.1](#)).

- (in Cohort 1) Disease progression after crizotinib as the only ALK inhibitor. Approximately 66 patients will be enrolled to this cohort.
- (in Cohort 2) Disease progression after one ALK inhibitor other than crizotinib. Approximately 34 patients will be enrolled to this cohort.

Figure 1. Study B7461024 Design

A cycle duration will be 3 weeks (**21 days**) and will always be considered 3 weeks irrespective of any dose delays/dosing interruptions or missed doses which may affect nominal days of each cycle.

Study treatment may continue until confirmed disease progression assessed by ICR, subject refusal, subject lost to follow-up, unacceptable toxicity, or the study is terminated by the sponsor, whichever comes first (see [Section 6.4](#) Subject Withdrawal).

Subjects who develop radiological disease progression confirmed by ICR assessment but are otherwise continuing to derive clinical benefit from study treatment will be eligible to continue with the treatment they have been assigned to, provided that the treating physician has determined that the benefit/risk for doing so is favorable. See [Section 7.2](#) for details on expedited ICR assessment of disease progression.

Details of the study treatment forms and packaging and recommendations for dose modifications are included in the Study Treatment [Section 5](#) of the protocol.

4. SUBJECT ELIGIBILITY CRITERIA

This study can fulfill its objectives only if appropriate subjects are enrolled. The following eligibility criteria are designed to select subjects for whom participation in the study is considered appropriate. All relevant medical and nonmedical conditions should be taken into consideration when deciding whether a particular subject is suitable for this protocol.

Subject eligibility should be reviewed and documented by an appropriate member of the investigator's study team before subjects are included in the study.

4.1. Inclusion Criteria

Subjects must meet all of the following inclusion criteria to be eligible for enrollment into the study:

1. Evidence of histologically or cytologically confirmed diagnosis of locally advanced or metastatic ALK-positive NSCLC where ALK status has been previously established by the Ventana ALK (D5F3) CDx Assay (Roche Diagnostics), the Vysis ALK Break Apart FISH Probe Kit (Abbott Molecular), or the EML4-ALK Fusion Gene Detection Kit (AmoyDx).
2. Subject should have:
 - a. (in Cohort 1) Disease progression after crizotinib as the only ALK inhibitor;
 - b. (in Cohort 2) Disease progression after one ALK inhibitor other than crizotinib, with or without prior crizotinib.
3. Prior treatment with an ALK inhibitor must have completed ≥ 5 half-lives prior to study entry.
4. All Subjects must have at least 1 measurable extracranial target lesion according to RECIST v1.1 that has not been previously irradiated. CNS metastases are allowed if:
 - a. Asymptomatic: either not currently requiring corticosteroid treatment, or on a stable or decreasing dose of ≤ 10 mg QD prednisone or equivalent; or
 - b. Previously diagnosed and treatment has been completed with full recovery from the acute effects of radiation therapy or surgery prior to enrollment, and if corticosteroid treatment for these metastases has been withdrawn for at least 4 weeks with neurological stability.
5. Eastern Cooperative Oncology Group performance status (ECOG PS) 0, 1, or 2.
6. Age ≥ 18 years (or ≥ 20 years as required by local regulation).
7. Adequate bone marrow functions:
 - a. Absolute Neutrophil Count (ANC) $\geq 1,500/\text{mm}^3$ or $\geq 1.5 \times 10^9/\text{L}$;
 - b. Platelets $\geq 100,000/\text{mm}^3$ or $\geq 100 \times 10^9/\text{L}$;
 - c. Hemoglobin ≥ 9 g/dL.

8. Adequate pancreatic function:
 - a. Serum total amylase ≤ 1.5 x upper limit of normal (ULN);*
 - b. Serum lipase ≤ 1.5 x ULN.

*if total amylase > 1.5 x ULN, but pancreatic amylase is within the ULN, then subject may be enrolled.
9. Adequate renal function:
 - a. Serum creatinine ≤ 1.5 x ULN or estimated creatinine clearance ≥ 60 mL/min as calculated using the method standard for the institution.
10. Adequate liver function:
 - a. Total serum bilirubin ≤ 1.5 x ULN;
 - b. Aspartate Aminotransferase (AST) and Alanine Aminotransferase (ALT) ≤ 2.5 x ULN (≤ 5.0 x ULN in case of liver metastases).
11. Acute effects of prior radiotherapy and chemotherapy resolved to baseline severity or to National Cancer Institute (NCI) Common Terminology Criteria for Adverse Events (CTCAE) Grade ≤ 1 except for AEs that in the investigator's judgment do not constitute a safety risk for the subject.
12. Serum or urine pregnancy test (for females of childbearing potential) negative at screening. Female subjects of non-childbearing potential must meet at least 1 of the following criteria:
 - a. Achieved postmenopausal status, defined as follows: cessation of regular menses for at least 12 consecutive months with no alternative pathological or physiological cause (which may be confirmed with a serum follicle-stimulating hormone (FSH) level confirming the postmenopausal state if appropriate);
 - b. Have undergone a documented hysterectomy and/or bilateral oophorectomy;
 - c. Have medically confirmed ovarian failure.

All other female subjects (including female subjects with tubal ligations) are considered to be of childbearing potential.
13. Evidence of a personally signed and dated informed consent document indicating that the subject (or a legally acceptable representative) has been informed of all pertinent aspects of the study.

14. Willing and able to comply with the study scheduled visits, treatment plans, laboratory tests, and other procedures.

4.2. Exclusion Criteria

Subjects with any of the following characteristics/conditions will not be included in the study:

1. More than 1 prior chemotherapy regimen prior to enrollment in advanced/metastatic setting.

If disease recurred/relapsed within the adjuvant chemotherapy treatment or ≤ 6 months after the completion of the adjuvant chemotherapy, then the adjuvant chemotherapy is considered as the first line systemic chemotherapy to the disease.

2. Systemic anti-cancer therapy completed within a minimum of 5 half-lives of study enrollment.
3. Prior therapy with an antibody or drug specifically targeting T-cell co-stimulation or immune checkpoint pathways, including, but not limited to, anti-programmed cell death protein 1 (anti-PD-1), anti-programmed cell death protein ligand 1 (anti-PD-L1), anti-PD-L2, anti-cluster of differentiation 137 (anti-CD137), or anti-cytotoxic T lymphocyte associated antigen 4 (anti-CTLA-4) antibody.
4. Known epidermal growth factor receptor (EGFR) activating mutations; known prior therapy with EGFR TKI(s) (the prior treatment with brigatinib is allowed as an ALK TKI).
5. Major surgery within 4 weeks prior to enrollment. Minor surgical procedures (eg, port insertion) are not excluded, but sufficient time should have passed for adequate wound healing.
6. Radiation therapy within 2 weeks prior to enrollment. Palliative radiation must have been completed at least 48 hours prior to enrollment. Stereotactic or partial brain irradiation must have completed at least 2 weeks prior to enrollment. Whole brain irradiation must have completed at least 4 weeks prior to enrollment.
7. Spinal cord compression unless the subject has good pain control attained through therapy, and there is complete recovery of neurological function for the 4 weeks prior to enrollment.
8. Gastrointestinal abnormalities, including inability to take oral medication; requirement for intravenous alimentation; prior surgical procedures affecting absorption including total gastric resection or lap band; active inflammatory gastrointestinal disease, chronic diarrhea, symptomatic diverticular disease; treatment for active peptic ulcer disease in the past 6 months; malabsorption syndromes.

9. Known prior or suspected severe hypersensitivity to lorlatinib or any component in the formulation; known prior therapy with lorlatinib.
10. Active and clinically significant bacterial, fungal, or viral infection including hepatitis B virus (HBV), hepatitis C virus (HCV), known human immunodeficiency virus (HIV) or acquired immunodeficiency syndrome (AIDS)-related illness.
11. Clinically significant cardiovascular disease (both arterial and venous) and non-vascular cardiac conditions, (active or within 3 months prior to enrollment, which may include, but not are limited to:
 - Arterial disease such as cerebral vascular accident/stroke (including transient ischemic attack -TIA), myocardial infarction, unstable angina;
 - Venous diseases such as cerebral venous thrombosis, symptomatic pulmonary embolism;
 - Nonvascular cardiac disease such as congestive heart failure (New York Heart Association Classification Class \geq II), second- degree or third-degree atrioventricular block (unless paced) or any AV block with PR interval >220 msec; or
 - Ongoing cardiac dysrhythmias of CTCAE Grade ≥ 2 , uncontrolled atrial fibrillation of any grade, bradycardia defined as <50 bpm (unless subject is otherwise healthy such as long-distance runners, etc.), machine-read electrocardiogram (ECG) with QTc >470 msec, or congenital long QT syndrome.
12. Subject with predisposing characteristics for acute pancreatitis according to investigator judgment, including but not limited to uncontrolled hyperglycemia, current gallstone disease, in the last month prior to enrollment.
13. History of extensive, disseminated, bilateral or presence of Grade 3 or 4 interstitial fibrosis or interstitial lung disease including a history of pneumonitis, hypersensitivity pneumonitis, interstitial pneumonia, interstitial lung disease, obliterative bronchiolitis and pulmonary fibrosis.
14. Evidence of active malignancy (other than NSCLC, non-melanoma skin cancer, or localized and presumed cured prostate cancer or any in situ cancer which does not currently require treatment) within the last 3 years prior to enrollment.
15. Concurrent use of any of the following food or drugs (consult the sponsor if in doubt whether a food or a drug falls into any of the above categories) within 12 days prior to the first dose of administration of lorlatinib:

- a. Known strong CYP3A inhibitors (eg, strong CYP3A inhibitors: grapefruit juice or grapefruit/grapefruit related citrus fruits [eg, Seville oranges, pomelos], boceprevir, cobicistat, conivaptan, itraconazole, ketoconazole, posaconazole, ritonavir alone and with danoprevir or elvitegravir or indinavir or lopinavir or paritaprevir or ombitasvir or dasabuvir or saquinavir or tipranavir, telaprevir, troleandomycin, and voriconazole). The topical use of these medications (if applicable), such as 2% ketoconazole cream, is allowed;
 - b. Known CYP3A substrates with narrow therapeutic index, such as astemizole*, terfenadine*, cisapride*, pimozone, quinidine, tacrolimus, cyclosporine, sirolimus, alfentanil, fentanyl (including transdermal patch) or ergot alkaloids (ergotamine, dihydroergotamine) (*withdrawn from US market);
 - c. Known strong CYP3A inducers (eg, carbamazepine, enzalutamide, mitotane, phenytoin, rifampin, St. John's Wort);
 - d. Known P-glycoprotein (P-gp) substrates with a narrow therapeutic index (eg, digoxin).
16. Other severe acute or chronic medical or psychiatric condition, including recent (within the past year) or active suicidal ideation or behavior, or laboratory abnormality that may increase the risk associated with study participation or investigational product administration or may interfere with the interpretation of study results and, in the judgment of the investigator and/or the sponsor, would make the subject inappropriate for entry into this study.
17. Subject who are investigational site staff members directly involved in the conduct of the study and their family members, site staff members otherwise supervised by the investigator, or subjects who are Pfizer employees, including their family members, directly involved in the conduct of the study.
18. Participation in other studies involving investigational drug(s) within 2 weeks prior to study entry and/or during study participation.
19. Pregnant female subjects; breastfeeding female subjects; fertile male subjects and female subjects of childbearing potential who are unwilling or unable to use a highly effective method of contraception as outlined in this protocol for the duration of the study and for at least 97 days if male or 21 days if female, after the last dose of investigational product.

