1.2.3.3.2. Clinical Drug-Drug Interaction

In vitro, lorlatinib is a time-dependent inhibitor as well as an inducer of CYP3A4/5 and activates the human pregnane X receptor (hPXR), with a net induction effect on CYP3A4/5 in vivo. Coadministration of lorlatinib and midazolam (MDZ) in patients resulted in decreased mean oral MDZ (a CYP3A4 substrate) AUC and C_{max} after 25 mg and 150 mg QD lorlatinib dosing, compared with those for MDZ alone. Coadministration of lorlatinib with CYP3A4/5 substrates with narrow therapeutic indices should be avoided.

Coadministration of 200 mg daily doses of itraconazole (a strong CYP3A4/5 inhibitor) with a single 100 mg of lorlatinib increased lorlatinib AUC_{inf} by 42% and C_{max} by 24%. An alternative concomitant medicinal product with less potential to inhibit CYP3A4 should be considered. If a strong CYP3A4/5 inhibitor must be coadministered, a dose reduction of lorlatinib from the starting dose of 100 mg QD to 75 mg QD is recommended.

Coadministration of 600 mg daily doses of rifampin (a strong CYP3A4/5 inducer) with a single 100 mg dose of lorlatinib decreased lorlatinib AUC_{inf} by 85% and C_{max} by 76%. Concomitant administration of lorlatinib and rifampin led to elevated AST and ALT levels in all subjects. Use of strong CYP3A4/5 inducers with lorlatinib is contraindicated. Avoid concomitant use with moderate CYP3A4/5 inducers if possible, as they may also reduce lorlatinib plasma concentrations.

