5.1. Allocation to Treatment

The investigator's knowledge of the treatment should not influence the decision to enroll a particular subject or affect the order in which subjects are enrolled.

A subject must sign an informed consent document (ICD) before being evaluated for study entry. Once a subject who has met inclusion and exclusion criteria has provided a signed ICD, allocation of subjects to lorlatinib treatment will proceed through the use of an interactive response technology (IRT) system (interactive Web-based response [IWR]). The site personnel (study coordinator or specified designee) will be required to enter or select information including but not limited to the user's identification (ID) and password, the protocol number, and the subject number. The site personnel will then be provided with a treatment assignment, randomization number, and dispensable unit (DU) or container number when investigational product is being supplied via the IRT system. The IRT system will provide a confirmation report containing the subject number, randomization number, and DU or container number assigned. The confirmation report must be stored in the site's files.

The study-specific IRT reference manual will provide the contact information and further details on the use of the IRT system.

Qualified subjects will be enrolled to the study to receive lorlatinib monotherapy at the RP2D of 100 mg QD, administered as 4×25 mg oral tablets, continuously. Study treatment should be initiated preferably on the randomization day but no later than 1 day after randomization.

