5.9.1. Inhibitors and Inducers of CYP Enzymes

The list of food and drugs to be avoided provided below may not be fully exhaustive. Consult the sponsor when in doubt whether a food or a drug falls into any of the categories below.

The in vitro studies have demonstrated that CYP3A, and UGT1A4 are primarily involved in the metabolism of lorlatinib, with additional minor contributions from CYP2C19 and CYP2C8. Inhibition or induction of the above enzymes may result in potential alteration of lorlatinib systemic exposure.

Initial in vitro assessment for inhibition and induction drug-drug interaction potential indicated that lorlatinib is a time-dependent inhibitor of CYP 3A and also an inducer of CYP3A and CYP2B6. At substantially higher concentrations than those observed clinically, lorlatinib also inhibited CYP2C9 in in vitro studies.

To protect subject safety, the following cautions are provided:

- Lorlatinib metabolism may be inhibited by strong CYP3A inhibitors leading to a potential increase in lorlatinib toxicities. Coadministration of strong CYP3A inhibitors (eg, boceprevir, cobicistat, conivaptan, itraconazole, ketoconazole, and posaconazole, ritonavir alone and with danoprevir or elvitegravir or indinavir or lopinavir or paritaprevir or ombitasvir or dasabuvir or saquinavir or tipranavir, telaprevir, troleandomycin, and voriconazole, grapefruit juice or grapefruit/grapefruit-related citrus fruits [eg, Seville oranges, pomelos]) is not recommended and alternate medications should be considered. If the concomitant use of the strong CYP3A inhibitor cannot be avoided, reduce the starting dose of lorlatinib from 100 mg orally once daily to 75 mg orally once daily. In patients who have had a dose reduction to 75 mg orally once daily due to adverse reactions and who initiate a strong CYP3A inhibitor, reduce the lorlatinib dose to 50 mg orally once daily. If concomitant use of a strong CYP3A inhibitor is discontinued, increase the lorlatinib dose (after 3 plasma half-lives of the strong CYP3A inhibitor) to the dose that was used before starting the strong inhibitor.

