- Use of strong CYP3A inducers with lorlatinib is contraindicated. Lorlatinib metabolism may be induced when taking strong CYP3A inducers (eg, carbamazepine, enzalutamide, mitotane, phenytoin, rifampin, St. John's Wort) resulting in reduced plasma concentrations. Furthermore, when lorlatinib was coadministered with rifampin, increases in AST and ALT were noted. Discontinue strong CYP3A inducers for 3 plasma half-lives of the strong CYP3A inducer prior to initiating lorlatinib and until lorlatinib is permanently discontinued. In addition, use with moderate CYP3A inducers (eg, bosentan, efavirenz, etravirine, modafinil) should be avoided due to the potential reduction in lorlatinib exposure.
- Lorlatinib induces CYP2B6 (in vitro) so concurrent use of drugs that are CYP2B6 substrates, such as bupropion and efavirenz, may have less effect. Concomitant CYP2B6 substrates should be used with caution, as the net clinical effect of lorlatinib on CYP2B6 is currently being investigated.
- Lorlatinib induces CYP3A (in vivo) which may lead to a decreased effect of concurrently used CYP3A substrates (eg. hormonal contraceptives etc.). Coadministration of lorlatinib with CYP3A substrates with a narrow therapeutic index (NTI) such as alfentanil, fentanyl (including transdermal patch), astemizole*, cisapride*, cyclosporine, dihydroergotamine, ergotamine, pimozone, quinidine, sirolimus, tacrolimus, terfenadine* (*withdrawn from US market) is not permitted at study entry. However, if it is absolutely necessary to use, sponsor approval is required and the dose of the CYP3A substrate may need to be increased. The NTI CYP3A substrate should be started only after at least 14 days of continuous lorlatinib dosing. If there is a change in the lorlatinib dosing regimen such as a dosing interruption or dose reduction, the administration of the NTI CYP3A substrate should be stopped and resumed at a readjusted dose only after at least 14 days of resumed lorlatinib dosing.

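### Exclusion 15c and Section 5.9.1 set different washouts for strong CYP3A inducers before lorlatinib starts, and Section 5.9.1 does not say whether its reduced starting dose with a strong inhibitor applies at entry

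*Protocol*

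**What the plan says.** **Entry rule.** Protocol Section 4.2 opens with an absolute condition: "Subjects with any of the following characteristics/conditions will not be included in the study". Exclusion 15 then covers use of four drug classes "within 12 days prior to the first dose of administration of lorlatinib". Item 15a is strong CYP3A inhibitors, with only topical use allowed. Item 15c is the inducers: "Known strong CYP3A inducers (eg, carbamazepine, enzalutamide, mitotane, phenytoin, rifampin, St. John's Wort".

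**Section 5.9.1, inducers.** The section calls use of these drugs with lorlatinib contraindicated, names the same six examples as 15c, and instructs: "Discontinue strong CYP3A inducers for 3 plasma half-lives of the strong CYP3A inducer prior to initiating lorlatinib".

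**Section 5.9.1, inhibitors.** Co-administration is not recommended. Where it cannot be avoided, the instruction is to "reduce the starting dose of lorlatinib from 100 mg orally once daily to 75 mg orally once daily". Section 1.2.3.3.2 carries a similar sentence.

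**Starting dose and timing.** Section 5.1: "Qualified subjects will be enrolled to the study to receive lorlatinib monotherapy at the RP2D of 100 mg QD". The protocol summary says the same of all enrolled patients. Neither mentions a lower start. Section 5.1 also asks that treatment begin preferably on the day of randomization, and at most one day later.

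**The concern.** Both inducer rules act before the first dose and count back from it, and they cover the same drugs. A fixed number of days and a multiple of each drug's half-life cannot be the same rule. A site that checks eligibility against Section 4.2 can therefore enrol a patient whom Section 5.9.1 would not yet allow to start. Exclusion 15 does not point to Section 5.9.1, and nothing says that both intervals must be met.

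The inhibitor bullet raises a separate question of scope. A reduced starting dose suggests a patient who is on the inhibitor when lorlatinib begins, but Exclusion 15a does not admit such a patient.

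At stake are the safety of the few patients who could start too soon by the protocol's own standard, and whether sites apply one entry rule and classify eligibility deviations alike.

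**Working it through.** The plan gives no figure to reproduce on this point. The check is a side-by-side reading plus one line of arithmetic.

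**1. Inducer washout.** Inputs: W1 = 12 days (Exclusion 15) and W2 = 3 × t½ (Section 5.9.1). They are equal when 3 × t½ = 12, so t½ = 12 / 3 = 4 days.

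The documents give no inducer half-lives, so the values below are assumptions that show the range. The last column is the fraction of inducer left at 12 days, 0.5^(12 / t½), assuming first-order elimination. Under Section 5.9.1 that fraction at the end of washout is always 0.5³ = 12.5%. It describes the drug in plasma, not the induction that remains.

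| Assumed t½ (days) | Section 5.9.1 (days) | Exclusion 15 (days) | Longer rule | Left at 12 days |
|---|---|---|---|---|
| 1 | 3 | 12 | Exclusion 15, by 9 | 0.02% |
| 2 | 6 | 12 | Exclusion 15, by 6 | 1.6% |
| 4 | 12 | 12 | equal | 12.5% |
| 6 | 18 | 12 | Section 5.9.1, by 6 | 25% |
| 10 | 30 | 12 | Section 5.9.1, by 18 | 43.5% |
| 20 | 60 | 12 | Section 5.9.1, by 48 | 66.0% |

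**2. Why the upper rows matter.** Take t½ = 6 days and a last inducer dose 13 days ago. Exclusion 15 is passed, because 13 > 12. Section 5.9.1 still requires 18 − 13 = 5 more days. If the site has already randomized the patient, Section 5.1 allows 1 day. The site can then keep Section 5.1 or Section 5.9.1, but not both.

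**3. Scope of the inhibitor bullet in Section 5.9.1.** Read sentence by sentence:

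- The reduced starting dose points to entry.
- The next sentence concerns patients already reduced to 75 mg for adverse reactions who then begin an inhibitor. That is on-treatment.
- The last sentence restores the dose in use before the inhibitor was begun. That presupposes that lorlatinib came first; a patient who began at 75 mg has no earlier dose to return to.
- The bullets on narrow-therapeutic-index CYP3A substrates and P-gp substrates each state a bar at study entry. The inhibitor bullet does not.

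The bullet fits neither reading cleanly.

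**4. Primary test.** The rule of 28 responses in 66 patients gives an exact one-sided error of 0.0216 at 30% and power of 0.912 at 50%, in line with the planned 0.025 and 90%. Neither washout rule nor starting dose enters this calculation.

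**The case against.** The best reply is that Section 4.2 alone decides eligibility. Section 5.9.1 sits under concomitant treatment and can admit no one. Below a 4-day half-life this is a complete answer: Exclusion 15 is the longer interval and it governs. Above 4 days, a site that reads both sections can satisfy both by observing the longer interval. That is true, but no passage tells it to. It is also fair that the documents show no listed inducer to have a half-life above 4 days, so the number of drugs affected is unknown.

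On inhibitors, the on-treatment reading is the more natural one for most of the bullet, and leaving out an entry bar there is not permission to enrol. Only the starting-dose wording stands against it.

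A reader might infer more than the documents support:

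- **That one patient could be excluded, started at 100 mg or started at 75 mg depending on the page.** Section 5.1 covers only subjects who have already qualified, so it is not a competing entry rule. A current inhibitor user faces exclusion or 75 mg. A former inducer user faces exclusion, waiting or the usual start; 75 mg never arises.
- **That the rifampin findings measure the harm.** Section 1.2.3.3.2 reports an 85% fall in AUCinf and says "Concomitant administration of lorlatinib and rifampin led to elevated AST and ALT levels in all subjects", but this was daily co-administration, which neither section permits. It does not measure the difference between two washouts.
- **That ORR would be distorted.** Section 1.2.3.3.3 reports no exposure-response relationship for ORR.
- **That exposure tables would mislead.** A constant 75 mg gives a relative dose intensity of 525 / 700 = 75% under SAP 6.4.3.1. That is the formula working as defined, and a 75 mg start with an inhibitor at entry would need a breach of Exclusion 15a.

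**Conclusion.** The point holds as an internal inconsistency in wording. The inducer washout is stated in two ways that agree only at a 4-day half-life. For longer half-lives, Exclusion 15c applied as written clears a patient whom Section 5.9.1 bars from starting. At assumed half-lives of 6 to 20 days the shortfall is 6 to 48 days; whether any drug in use falls in that range cannot be told from the documents. The inhibitor part is weaker: an ambiguity of scope rather than a firm contradiction.

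Few patients are likely to be affected. This is a judgement, since the documents give no frequency of such co-medication. The primary analysis is unchanged: it uses every enrolled patient who received a dose, and even the per-protocol set carries no condition on co-medication or starting dose. The case for acting is patient safety and uniform eligibility, not the validity of the ORR test.

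**What to change.** The sponsor should reconcile the passages and choose the rule and dose; none is proposed here.

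1. State one washout rule for strong CYP3A inducers, in the same words and with the same anchor date, in Exclusion 15c and in Section 5.9.1.
2. In the strong-inhibitor bullet of Section 5.9.1, state whether the starting-dose sentence applies at entry or only to inhibitors begun on study. Then align Exclusion 15a, Section 1.2.3.3.2, Section 5.1 and the treatment paragraph of the protocol summary with that statement.

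The cost is wording in these sections and a note to sites. No new data, procedures or analyses are needed; the deviation summary already planned in SAP 6.4.2.2 can record departures from the single rule. The downside is that some patients may wait longer or be screened out. If enrolment has closed, the clarification still settles which entries count as deviations.
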